6.4 Vital Signs

All vital sign measurements will be taken after the subject is supine for 5 minutes.

Vital signs (including blood pressure and pulse [radial or brachial to be measured over 30 seconds if performed manually], respiration rate, and body temperature (oral).

Vital signs, respiration rate, and body temperature will be measured at screening. Vital signs will be measured on Day -1, prior to administration of rivaroxaban on Days 1-3, 30 minutes prior to study drug, at 1, 4, 8 and 24 hours post-study drug. Please see below for tolerance window to perform vital sign assessments:

Vital Signs Tolerance Window

Vital Sign Time Point	Tolerance Window
Pre-dose	-60 minutes to 0 hour
>0 hour - 4 hour	-10 minutes to +10 minutes
>4 hour - 12 hour	-20 minutes to +20 minutes
>12 hour - 24 hour	-30 minutes to +30 minutes
Study Exit/Early Termination	-30 minutes to +30 minutes

Vital signs, respiratory rate, and body temperature will be re-assessed at the discretion of the investigator if warranted by the subject's condition and/or in the following situations:

- Systolic blood pressure less than 90 mmHg or greater than 180 mmHg
- Diastolic blood pressure less than 50 mmHg or greater than 100 mmHg
- Pulse less than 40 beats per minute or greater than 110 beats per minute
- Respiratory rate less than 10 breaths per minute or greater than 30 breaths per minute
- Body temperature less than 36.1°C (97.0°F) or greater than 37.3°C (99.2°F)

An abnormal vital sign that is considered clinically significant by the Investigator will be recorded as an adverse event. Additional vital sign measurements may be conducted at any time throughout the study, if deemed necessary by the Investigator.

6.5 Clinical Laboratory Tests

Blood and urine samples for safety laboratory tests will be collected at screening, at check-in, and prior to discharge from the clinical site. Safety laboratory tests may also be done at any time during the study at the discretion of the Investigator to monitor AEs. Subjects will be in a seated or supine position during blood collection.

6.5.1 Fecal Occult Blood Tests

Fecal occult blood tests will be done at check-in. Fecal occult blood kits will be given to all subjects at screening to provide stool samples for testing at check-in. In the event occult blood kits are not returned, a rectal exam for stool sample may be performed at the

discretion of the Investigator. Occult blood test results must be negative during check-in to continue study participation.

Additional fecal occult blood testing may be conducted at any time throughout the study, if deemed necessary by the Investigator.

6.5.2 Laboratory Parameters

Values for the clinical laboratory tests listed below will be determined by accredited laboratory facility(ies).

CLINICAL CHEMISTRY	HEMATOLOGY
The following clinical chemistry tests will be performed at screening, check-in, and discharge from the study:	The following hematology tests will be performed at screening, check-in, and discharge from the study:
Alanine aminotransferase (ALT)	Hematocrit
Albumin(ALB)	Hemoglobin
Aspartate aminotransferase (AST)	Platelet count
Blood urea nitrogen (BUN)	RBC
Calcium	WBC / with differential
Chloride	PT-PTT
CO ²	
Creatinine(CR)	URINALYSIS
Direct bilirubin (DBIL)	The following urinalysis tests will be performed at screening, check-in, and discharge from the study:
Glucose	
Indirect bilirubin (IBIL)	Appearance
Lactose dehydrogenase (LDH)	Bilirubin
Magnesium	Blood
Potassium	Color
Sodium	Creatinine
Total bilirubin (TBIL)	Glucose
Total Protein	Ketones
	Microscopic examination
	Occult Blood
	pH
	Protein
	Specific gravity
PREGNANCY SCREEN** (females only)	VIRAL SCREEN*** (to be performed at screening only):
Urine pregnancy test will be done at screening and discharge. Serum pregnancy test will be done at check-in on Day -1. Serum FSH and estradiol tests will be done on post-menopausal females at screening and check-in on Day -1 **the urine pregnancy tests may be performed in-clinic using CLIA-waived marketed kits.	HBsAg HIV antibody test HCV antibody test
Saliva Alcohol Test - (to be performed at screening and at check-in using CLIA -waived marketed kits)	Urine Drug Screen – (to be performed at screening and check-in using CLIA –waived marketed kits)

6.5.3 Experimental Safety Biomarker Assessment

Two aliquots of citrated plasma (1 ml each) for experimental safety biomarker assessments (e.g. D-Dimer, F1.2 tests) will be collected at pre-rivaroxaban (within 1 hr. prior to dosing) on Day 1, and at 3.75 and 8 hrs. post-rivaroxaban on Day 3. Experimental safety biomarker assessment will only be performed at the discretion of the Principal Investigator.

6.6 Electrocardiograms

A resting 12-lead electrocardiogram will be performed at screening, check-in, after administration of rivaroxaban, and prior to discharge from the clinic site. Parameters assessed will include ventricular rate (bpm), PR interval (msec), QRS duration (msec), QT interval (msec) and QTc interval (msec). Additional ECGs may be performed at the discretion of the Principal Investigator.

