- d. A complete physical examination will be performed at screening. An abbreviated physical examination will be performed at check-in and prior to discharge from the clinical site.
- e. Vital signs (blood pressure and heart rate), respiration rate, and temperature will be measured at screening and check-in. Vital signs will be measured prior to administration of rivaroxaban, within 30 minutes prior to study drug dosing, and at 1, 4, 8 and 24 hrs. post-study drug dosing.
- f. Safety laboratory tests (hematology, blood chemistry and urinalysis) will be performed at screening, at check-in (if the screening lab are not conducted within 3 weeks), and prior to discharge. Blood samples for experimental safety biomarker assessments will be collected at pre-rivaroxaban on day 1 and post-rivaroxaban 3.75 and 5 hours on day 3. Fecal occult blood tests will be performed at check-in. Occult blood kits will be given to subjects at screening and should be returned at check-in. Occult fecal blood tests must be negative at check-in to continue study participation. In the event an occult blood kit is not returned, a rectal exam for stool

sample may be performed at the discretion of the Investigator. Following the treatment period, coagulation parameters (WBCT result) must be not clinically significant prior to discharge.

- g. Urine drug and saliva alcohol tests will be performed at screening and at check-in. A blood sample will be taken to assess the presence of HbsAg, HCV-Ab and HIV at screening.
- h. Electrocardiograms (12-lead) will be performed at screening, check-in, after receiving rivaroxaban on day 1-3, and prior to discharge. Additional ECG may be performed at PI discretion.
- i. Urine pregnancy testing will be performed for all women at screening and at discharge. Serum pregnancy test will be done for all women at check-in on Day -1.
- j. Subjects will be admitted to the clinical site on Day -1 for baseline assessments and will remain confined until 24 hours after the study drug administration provided that, in the opinion of the Investigator, it is safe to be discharged.
- k. Rivaroxaban will be administered as a single 20 mg oral tablet after meal on Days 1-3 and followed 4 hours later by study drug injection on Day 3.

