1.2.4 PER977-02-001

PER977-02-001 was a randomized single-blind sequential group ascending ciraparantag reversal dose study in healthy volunteers who received a single dose of 60 mg edoxaban in the morning on Days 1-4 followed on Day 3 and Day 4 by a single IV dose of study drug. Five dose cohorts of 15 mg, 30 mg, 60 mg, 180 mg, and 360 mg ciraparantag (25 mg, 50 mg, 100 mg, 300 mg, and 600 mg ciraparantag acetate), respectively were planned and completed. Any subject who did not have a minimum increase in WBCT of 25% above baseline at the pre-study drug time point on Day 3 was discontinued from the study and replaced.

The pharmacokinetic results show that following 10-minute IV injection of ciraparantag on Day 3 and Day 4, serum PER977 C_{max} were typically observed at 0.25 hour (i.e., at the first postdose time point measured five minutes after the end of the 10-minute injection). Ciraparantag was then rapidly eliminated, with mean half-life ($t_{1/2}$) ranging from 0.207 to 0.336 hour (12.4 to 20.2 minutes). Clearance and volumes of distribution remained relatively constant across most doses and on both Days 3 and 4. Over the 24-fold dose range from 15 mg to 360 mg, ciraparantag C_{max} and total exposures ($AUC_{(0-inf)}$ and $AUC_{(0-last)}$) increased approximately proportionally to the dose increase. However, the

90% confidence interval (CI) of the slope for Day 4 AUC_(0-last) were completely above the predefined (0.9298, 1.0702) critical region; and the upper bounds of the 90% CI of the slopes for other exposure parameters on Day 3 and Day 4 were just above the upper limit of the critical region. Dose-proportionality thus could not be statistically concluded.

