5.7.3 Lifestyle Restrictions

During the study, subjects will be advised against using manual razors and dental flosses. Electric razors and soft toothbrushes will be allowed.

Subjects will not perform any physical activity outside of their normal living activities and will not engage in strenuous activity from screening to study completion.

Except when ECGs must be taken in supine position, subjects will remain in the semi-erect or upright position with minimal ambulation (i.e. only to and from the washroom or for study procedures) for the first 8 hours after study drug dosing on Day 3.

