7.2.4 Day 3 Procedures

7.2.4.1 Pre-study drug

The following activities and/or assessments will be performed on Day 3 before administration of study drug in all subjects:

- Administration of a single 20 mg dose of rivaroxaban after breakfast; Maintain fast for 4 hours after the rivaroxaban dosing (+90 minutes tolerance window to avoid conflict with intensive PK/PD assessment); Water allowed ad libitum
- An ECG and vital signs
- Blood draw for PK assessment of rivaroxaban and pre-study drug baseline
- Blood draw for WBCT measurement (triplicates at pre-rivaroxaban and post-rivaroxaban at 3.75 hrs.)
- Blood draw for experimental safety biomarker assessment
- Randomization
- AEs and concomitant medications will be recorded

7.2.4.2 Study Drug Administration: Time 0

The following activities and/or assessments will be performed in the order listed on Day 3 in all subjects:

- Vital signs
- I.V. administration of study drug (ciraparantag or placebo)
- AEs and concomitant medications will be recorded

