7.2.4.6 Post-study Drug: 1 hour

The following activities and/or assessments will be performed on Day 3 at 1 hour post administration of study drug in all subjects:

- Blood draw for WBCT (triplicates)
- Blood draw for PK samples for ciraparantag/metabolite and rivaroxaban
- Vital signs
- AEs and concomitant medications will be recorded

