#### **4.8.5 Resting 12-Lead ECG**

A resting 12-lead electrocardiogram will be performed at screening, after administration of rivaroxaban, and prior to discharge from the clinic site. Parameters assessed will include ventricular rate (bpm), PR interval (msec), QRS duration (msec), QT interval (msec) and QTc interval (msec). Additional ECGs may be performed at the discretion of the Principal Investigator.

All ECG results will be listed by subject and summarized by treatment.

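### No scheduled ECG falls between study drug and the discharge tracing about 24 hours later, so the scheduled ECGs cannot show acute PR, QRS or QTc effects during exposure

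*Protocol*

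**What the plan says.** Protocol 6.6 lists ECGs at screening, at check-in, "after administration of rivaroxaban, and prior to discharge from the clinic site". Footnote h of the Study Procedures table has them at screening, check-in, "after receiving rivaroxaban on day 1-3, and prior to discharge". Neither says on which side of study drug the Day 3 tracing falls, and study drug follows rivaroxaban by four hours.

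Section 7.2.4 settles the order. The Day 3 ECG appears in 7.2.4.1, among activities that "will be performed on Day 3 before administration of study drug in all subjects". The list in 7.2.4.2 has vital signs, the injection and adverse events. Sections 7.2.4.3 to 7.2.4.11 then give nine lists, from 15 minutes to 24 hours. The 7.2.4.6 list, for example, which "will be performed on Day 3 at 1 hour post administration of study drug", has WBCT, PK, vital signs and adverse events. None of the nine has an ECG. The next tracing is in 7.2.5, before discharge on Day 4, and footnote j keeps subjects in the unit until 24 hours after study drug. Further ECGs are left to the investigator's discretion.

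Section 5.7.3, on the first eight hours after study drug, says: "Except when ECGs must be taken in supine position, subjects will remain in the semi-erect or upright position".

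SAP 3.1.3 names the 12-lead ECG among the safety endpoints, and SAP 4.8.5 states: "All ECG results will be listed by subject and summarized by treatment". Under Protocol 5.9, ECG data go to the group that decides whether to expand a cohort, change the dose or stop.

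**The concern.** Safety and tolerability of ciraparantag is a primary objective in the protocol (secondary in SAP 2.2), and ECG is one of its named measures. A tracing taken before the drug, followed by one a day later, gives no interval measurement while a short-lived drug is in the blood. A by-treatment table from those two times would say nothing about an effect that rises and falls with concentration, yet a reader could take an unremarkable table as evidence that there was none. The same gap affects the ECG part of the dose-decision review. The text is also unclear: 5.7.3 allows for supine ECGs in a period for which 7.2.4 schedules none.

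**Working it through.** **Inputs**
- Ciraparantag mean half-life: 0.207 to 0.336 h (Protocol 1.2.4).
- BAP mean half-life: 0.527 to 1.76 h (1.2.4). BAP peaks 0.42 to 0.92 h after the start of a 10-minute injection (1.2.4).
- Peak concentrations at 180 mg: about 10704 ng/mL for ciraparantag and 700 ng/mL for BAP (1.2.5).
- Time 0 is the end of injection (6.8 and 7).

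**Reproducing the plan's figure.** 0.207 × 60 = 12.4 min and 0.336 × 60 = 20.2 min, as 1.2.4 states.

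**Half-lives elapsed at 24 h** (24 divided by the half-life)
- Ciraparantag: 24/0.336 = 71 and 24/0.207 = 116.
- BAP: 24/1.76 = 14 and 24/0.527 = 46.

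**Share of peak left**, as 2^(−t/half-life), taking a first-order decline from a peak at time 0
- Ciraparantag at 24 h: at most 3 × 10^−22, effectively zero from 10704 ng/mL.
- BAP at 24 h: at most 0.008%, about 0.05 ng/mL from 700 ng/mL. Counted from its own latest peak, 0.92 − 0.17 = 0.75 h after the end of injection, it is 23.25/1.76 = 13.2 half-lives, or about 0.01%.

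**Time to fall to 1% of peak** (half-life × log2(100), and log2(100) = 6.64)
- Ciraparantag: 1.4 to 2.2 h.
- BAP: 3.5 to 11.7 h.

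**Ciraparantag present at existing draw times**

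| Time after end of injection | Share of peak |
|---|---|
| 15 min | 43% to 60% |
| 30 min | 19% to 36% |
| 1 h | 3.5% to 12.7% |
| 4 h | at most 0.03% |

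BAP peaks between 0.42 − 0.17 = 0.25 h and 0.75 h after the end of injection, so a tracing at 15 to 30 minutes also falls at or near the metabolite's peak.

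**Sensitivity (assumptions)**
- If the Day 4 tracing, which has no stated clock time, came at 20 h: about 1 × 10^−18 of ciraparantag and 0.04% of BAP at the longest half-lives.
- If half-lives were three times the longest reported means: 7 × 10^−8 of ciraparantag and 4.3% of BAP at 24 h.

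Neither changes the conclusion.

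**The case against.** **Serum half-life is not duration of effect.** Section 1.2.1 reports WBCT reversal for 24 hours at 30 to 180 mg, while 1.2.5 gives a half-life of about 12 to 17 minutes. This stands. A reader might infer that the ECG summary cannot detect any effect of ciraparantag, or must look clean whatever the drug does. The documents do not support that: a persistent or delayed effect could appear on Day 4.

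**Earlier studies looked and found nothing.** PER977-01-001 used triplicate ECGs up to 180 mg, alone and after edoxaban, with no dose-related findings. PER977-01-002 (heparin) and PER977-02-001 (edoxaban) report no ECG or telemetry concern up to 360 mg. The four planned doses lie within that range, so sparse ECGs may be deliberate. This lowers the concern. It does not cover the rivaroxaban combination, and the protocol's summaries give neither the ECG times nor the ages of those subjects.

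**Other measurements exist.** Vital signs at 1, 4 and 8 hours give heart rate but not PR, QRS or QTc. Discretionary ECGs are unsystematic and likely to follow symptoms, so they give no sound contrast with placebo.

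**Little rests on the ECG table.** SAP 4.8.5 is descriptive, SAP 4.8 confines change from baseline to laboratory and vital-sign parameters, and the review in Protocol 5.9 also uses pharmacodynamic, adverse event and laboratory data. This stands. It would go too far to infer that a formal treatment comparison of intervals is planned and defeated, or that dose decisions rest on ECGs.

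**The inconsistency is mild.** The ordering rule in 6.8 fits the 3.75-hour and Day 4 draws. Section 5.7.3 is conditional and would fit discretionary ECGs. Both points are fair, but 5.7.3 concerns the post-study-drug hours specifically and should be squared with 7.2.4.

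**One tracing is imprecise.** With 12 active subjects per dose and 16 pooled placebo, and an assumed SD of QTc change of 10 to 15 ms, the 90% interval half-width is 1.706 × SD × √(1/12 + 1/16), or 6.5 to 9.8 ms. This supports description rather than testing.

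**Conclusion.** The point holds for scheduled ECGs and for acute effects concurrent with exposure. No scheduled tracing falls between the injection and discharge. By then 71 to 116 ciraparantag half-lives and 14 to 46 BAP half-lives have passed, against roughly 0.7 to 2.4 ciraparantag half-lives at the 15- and 30-minute draws (15/20.2 to 30/12.4). The conclusion rests on three assumptions: first-order decline at the reported mean half-lives, a Day 4 tracing at about 24 hours, and acute interval effects that follow concentration. It leaves the primary WBCT analysis untouched. It deserves correction because ECG is a named endpoint and feeds the dose review, and the schedule can be made informative without an extra tracing.

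**What to change.** 1. Reconcile Protocol 6.6, footnote h, 7.2.4 and 5.7.3, stating each ECG's time relative to rivaroxaban and to study drug. Include Day 2, where the 7.2.3 list names the ECG ahead of rivaroxaban while footnote h says after.
2. Keep the Day 3 pre-study-drug tracing as the same-day baseline. It already fits the SAP 3.5 definition (last value before study drug).
3. Move one of the Day 1 or Day 2 post-rivaroxaban tracings to Day 3, shortly after the end of injection, alongside the 15- to 30-minute PK and PD draws. Each subject still has six planned ECGs (screening, check-in, three during Days 1 to 3, discharge).
4. In SAP 4.8.5, summarise change from the Day 3 pre-study-drug value by treatment and by time relative to study drug, descriptively.

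The cost is protocol and SAP wording, one fewer rivaroxaban-only tracing and a busier 15- to 30-minute window. Adding a tracing instead of moving one would cost 64 more ECGs, one per planned subject.

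If the data are already collected, tabulate ECGs by time from study drug and state in the report that the scheduled ECGs do not assess effects during exposure.

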6.7 Dispensing Study Drug

All study drugs will be prepared by the CRO pharmacy or designated personnel.

6.7.1 Ciraparantag

The study pharmacist or designated personnel will calculate the final volume of ciraparantag. Ciraparantag should be prepared on the day of dosing and stored at room temperature at least 1 hour before administration. The appropriate volume of Ciraparantag Injection will be withdrawn from the supplied vials.

Throughout this protocol, the active study drug doses are expressed as active drug substance (ciraparantag) (previously study drug doses were expressed as ciraparantag acetate with a content of 10 mg/mL). The administered dose is based on a concentration of 6 mg/mL ciraparantag and translates to the following dose conversions:

Ciraparantag Acetate	Ciraparantag	Dose Volume
600 mg	360 mg	60 mL
300 mg	180 mg	30 mL
100 mg	60 mg	10 mL
50 mg	30 mg	5 mL
25 mg	15 mg	2.5 mL

Ciraparantag will be prepared and administered by IV injection over a minimum of 10 minutes.

All ciraparantag doses must be labeled with the study number and date.

Study drug may be prepared on the day of dosing and will have an expiration of 4 hours at room temperature or will be refrigerated at 2-8°C (36-46°F) until use. All prepared solutions must be used within 24 hours. All unused drugs will be returned to the pharmacy. A record must be kept of all discarded solutions.

6.7.2 Placebo

An equivalent volume of sterile 0.9% Sodium Chloride Injection, USP will be utilized as the placebo.

All placebo doses must be labeled with the study number and date.

Placebo may be prepared on the day of dosing and will have an expiration of 4 hours at room temperature or will be refrigerated at 2-8°C (36-46°F) until use. All prepared solutions must be used within 24 hours. A record must be kept of all discarded solutions.

6.7.3 Rivaroxaban

Rivaroxaban will be dispensed as one tablet in a container labeled with the study number, subject number and date. All unused tablets will be returned to the pharmacy.

6.8 Efficacy Assessments

Time 0 for all PK and PD assessments will be the end of the study drug injection. Where timing for assessments coincide, PD assessment(s) should be performed first, followed by PK assessment(s), and then ECGs, and vital signs will be performed. The tolerance window to complete PK and PD draws is as follow:

PK/PD Draw Tolerance Window

Sampling Time Point	Tolerance Window
Pre-dose	-60 minutes to 0 hour
>0 hour - 24 hour	-10 minutes to +10 minutes

Over the course of the study, the total estimated volume of blood to be sampled from each subjects for the combined PK, PD and safety evaluations is approximately 225 mL.

6.8.1 Pharmacokinetic Assessment

Blood samples for PK assessment of ciraparantag and its metabolite, and rivaroxaban, will be analyzed using LC/MS assay methodology.

Rivaroxaban PK time points:

A 4 mL blood sample in potassium EDTA will be collected for each PK assessment of rivaroxaban.

Day 3: pre-rivaroxaban (within 1 hr. prior to dosing), post-rivaroxaban at 3.75, 4.25, 4.5, 4.75, 5, 6, 8, 10, 12, and 28 hrs.

Ciraparantag PK time points:

Ciraparantag or placebo is administered 4 hrs. after the rivaroxaban dosing on day 3.

A 3 mL blood sample with no additive (i.e. serum sample) will be collected for each PK assessment of ciraparantag and its metabolite.

Day 3: pre-study drug (within 1 hr. prior to dosing of ciraparantag or placebo), post-study drug at 0.25, 0.5, 0.75, 1, 2, 4, 6, 8 and 24 hrs.

6.8.2 Pharmacodynamic Assessment

Blood samples (2 ml) for measuring of clotting time by WBCT will be collected at the following time points:

Day 3: pre-rivaroxaban (within 1 hr. prior to dosing) and post-rivaroxaban at 3.75 and post-study drug at 0.25, 0.5, 0.75, 1, 2, 4, 6, 8 and 24 hrs. (Only subjects with at least 25% increase of clotting time from pre-rivaroxaban level on day 3 will be randomized).

Triplet WBCT will be done pre-rivaroxaban, post-rivaroxaban at 3.75 hrs. and post-study drug at 1 hr.

6.9 Adverse Events Assessments

All AEs and SAEs will be captured by electronic data capture (EDC).

All AEs occurring after the subject signs the ICF up to the time of the Follow-up phone call, whether observed by the Investigator or reported by the subject, will be captured. If in the opinion of the Investigator or the sponsor, an AE meets the criteria of an SAE it is to be reported. SAEs occurring up to 30 calendar days post treatment should be reported. Any AEs and SAEs that occur after the specified reporting period should also be reported if in the opinion of the investigator, there is a reasonable possibility for a causal association with the study product.

Medical conditions (including laboratory values/vital signs that are out of range) that were diagnosed or known to exist prior to Informed Consent will be recorded as part of medical history. All SAEs are to be reported according to the procedures in Section [6.9.10 SAE Reporting-Procedure for Investigators](#). Report diagnosis as the AE or SAE term; when the diagnosis is unavailable, report signs and symptoms as individual entries of AE or SAE until the diagnosis becomes available. For events that are serious due to hospitalization, the reason for hospitalization must be reported as the serious adverse event (diagnosis or symptom requiring hospitalization). A procedure is not an AE or

SAE, but the reason for the procedure may be an AE or SAE. Pre-planned (prior to signing the Informed Consent Form) procedure or treatment requiring hospitalization for pre-existing conditions which do not worsen in severity should not be reported as SAEs. For deaths, the underlying or immediate cause of death should always be reported as an SAE. In addition, any serious, untoward event that may occur subsequent to the reporting period that the Investigator assesses as related to study drug should also be reported and managed as an SAE.

At each visit, the Investigator will determine whether any AEs have occurred by evaluating the subject. Adverse events may be directly observed, reported spontaneously by the subject or by questioning the subject at each study visit. Subjects should be questioned in a general way, without asking about the occurrence of any specific symptoms. All abnormal laboratory values must be appraised by the Investigator as to clinical significance. All abnormal laboratory values considered clinically significant by the Investigator must be recorded as an AE on the CRF, and if serious, reported as an SAE following the procedures in Section 6.9.10.

Investigator should follow subjects with AEs until the event has resolved or the condition has stabilized. In case of unresolved AEs including significant abnormal laboratory values at the end of study assessment, these events will be followed until resolution or until they become clinically not relevant.

6.9.1 Clinical Laboratory Abnormalities and Other Abnormal Assessments as Adverse Events or Serious Adverse Events

Laboratory abnormalities are usually not recorded as AEs or SAEs. However, laboratory abnormalities (e.g., clinical chemistry, hematology, and urinalysis) that require medical or surgical intervention or lead to study drug discontinuation must be recorded as an AE, as well as an SAE, if applicable. In addition, laboratory or other abnormal assessments (e.g., ECG or vital signs) that are associated with signs and/or symptoms must be recorded as an AE or SAE if they meet the definition of an AE (or SAE) as described in Section 6.9.3 and Section 6.9.4, respectively. For AEs associated with laboratory abnormalities, the event should be graded on the basis of the clinical severity in the context of the underlying conditions; this may or may not be in agreement with the grading of the laboratory abnormality.

